#### 6.4 Compliance to Treatment

The effective doses of study drugs received by each patient during the trial will be recorded. Treatments received by the patients in the control (standard of care) group will be recorded. Any concomitant medication that the participant receives during the participation in this study will also be recorded. Specifically, dose, posology, frequency of administration, start and end date and reason of use will be required and collected.

There is no contraindication to the use of concomitant supportive and prophylactic care medications as deemed necessary by the treating physicians, unless incompatible with the study drug. Since Reparixin is metabolized by CYP2C9 there could be a theoretic effect on drug availability by any medication that is a known inhibitor or inducer of CYP2C9. These medications are not considered incompatible with Reparixin, however, a list of such medications is provided below for the consideration of the investigators:

- CYP2C9 Inducers: rifampin, carbamezapine, aprepitant, bosentan, phenobarbital, St. John's Wort;
- CYP2C9 Inhibitors: amiodarone, fluconazole, miconazole, oxandrolone, capecitabine, cotrimoxazole, etravirine, fluvastatin, fluvoxamine, metronidazole, sulfinpyrazone, tigecycline, voriconazole, zafirlukast.

## 7 ASSESSMENTS AND PROCEDURES

## 7.1 Procedures

Potential study patients with confirmed COVID-19 diagnosis will be identified from those referring to the participating clinical sites for diagnosis and/or management. Screening will be performed and completed in consented patients and potential study patients will be treated. Each patient will be involved in the study for the entire duration of the hospital treatment and for a maximum of 31 days (one month) including the follow-up.

## 7.2 Efficacy assessments

Clinical parameters to assess the efficacy of the experimental treatment will be assessed according to the Statistical Analysis Plan (SAP) and the Schedule of Evaluations.

All the laboratory and clinical parameters, including radiography imaging assessments, will be collected based on the local procedures of the participating clinical sites.

The degree of dyspnea will be collected using the "Liker" and Visual Analogues (VAS) scales. The Liker scale is used as follows: the patient grades his current breathing compared to when he first started the drug (from -3 to 3). "0" = no change, "1" =minimally better, "2" =moderately better, "3" =markedly better, "-1" =minimally worse, "-2" =moderately worse, "-3" =markedly worse. The VAS scale is used as follows: the patient draws a horizontal line on an axial graph (from 0 to 100) to show the degree of how he feels about breathing. The number "0" equals the worst breathing the patient has ever felt and the number "100" equals the best he has ever felt.

All the clinical endpoints are listed in Section 3 of this protocol but may be implemented considering the adaptive nature of this clinical trial, at the end of phase 2 of at any given time following the advice of the Data Monitoring Committee (DMC). The SAP will be modified accordingly.

# 7.3 EVALUATION OF ADVERSE EVENTS AND SAFETY INFORMATION

## 7.3.1 DEFINITIONS

## **Adverse Event**

An Adverse Event (AE) is defined as any untoward medical occurrence in a patient or clinical investigation subject administered a medicinal product and which does not necessarily have a causal relationship with this treatment. An AE can therefore be any unfavourable and unintended sign (including an abnormal laboratory finding), symptom, or disease temporally associated with the use of a medicinal product, whether or not related to the medicinal product.

## **Adverse Drug Reaction**

An **Adverse Drug Reaction (ADR)** is defined as an adverse experience which is a reasonably likely to have been caused by the drug. Adverse events are to be considered unsuspected if the relationship to the study drug as described in the table in section 7.3.4 is none or unlikely; whereas any AE reported in the study having a possible, probable or highly probable relationship to study drug will be considered as an ADR. The definition covers also medication errors and uses outside what is foreseen in the protocol, including misuse and abuse of the product.

## **Serious Adverse Event**

A Serious Adverse Event (SAE) is defined as any untoward medical occurrence that at any dose:

• results in death,

- is life-threatening (i.e. the patient was at risk of death at the time of the event. It does not refer to an event which hypothetically might have caused death if it were more severe),
- requires inpatient hospitalization or prolongation of existing hospitalization,

NOTE: In general, hospitalization means that the individual remained at the hospital or emergency ward for observation and/or treatment (usually involving an overnight stay) that would not have been appropriate in the physician's office or an out-patient setting. Complications that occur during hospitalization are AEs. If a complication prolongs hospitalization or fulfills any other serious criteria, the event is serious. When in doubt as to whether "hospitalization" occurred, the event should be considered serious.

• results in persistent or significant disability/incapacity,

NOTE: This definition is not intended to include experiences of relatively minor medical significance such as uncomplicated headache, nausea, vomiting, diarrhea, influenza, or accidental trauma (e.g., sprained ankle) which may interfere or prevent everyday life functions, but do not constitute a substantial disruption.

- is a congenital anomaly/birth defect,
- is medically significant or important medical condition, i.e. an important medical event that based upon appropriate medical judgment, may jeopardize the patient and may require medical or surgical intervention to prevent one of the outcomes listed above.

An important medical condition is an event that may not result in death, be life-threatening, or require hospitalization but may be considered a SAE when, based upon appropriate medical judgment, it may jeopardize the patient and may require medical or surgical intervention to prevent one of the outcomes listed above. Examples of such medical events include allergic bronchospasm requiring intensive treatment in an emergency room or at home, blood dyscrasias or convulsions that do not result in patient hospitalization, or the development of drug dependency or drug abuse.

Death shall always be reported as SAE: anyway, death due to progression of disease would not have a causal relationship to the product, based on Investigator's assessment. The investigator should report the event immediately to the sponsor, but the sponsor will not report the event as expedited to regulatory authority. Cause of death shall always be specified when known.

#### **Unexpected Adverse Events**

An AE or ADR is considered unexpected if it is not listed in the Investigator Brochure (Reference Safety Information section) or in the applicable authorised Summary of Product Characteristics. An event is unexpected also when it is not listed at the specificity or severity that has been observed and listed in the Investigator Brochure. Events that are mentioned in the Investigator Brochure as occurring with a class of drugs or as anticipated from the pharmacological properties of the drug, but are not specifically mentioned as occurring with the particular drug under investigation are considered unexpected.

The determination of expectedness shall be made on the basis of the IB Reference Safety Information (RSI) section.

#### Suspected Serious Unexpected Adverse Reaction (SUSAR)

A suspected serious unexpected adverse reaction is defined as an adverse reaction that is both unexpected (not consistent with the applicable product information) and also meets the definition of a Serious Adverse Reaction.

## 7.3.2 MONITORING FOR ADVERSE EVENTS

During the study, the subject shall have the opportunity to spontaneously mention any problems and anyway the Investigator or appropriate designee should inquire about AEs by asking the standard questions:

- "Have you had any health problems since your last study visit?"
- "Have there been any changes in the medicines you take since your last study visit?"

AEs should be reported for any clinically relevant change in concomitant condition(s) that is the result of an untoward (unfavorable and unintended) change in a subject's medical health, regardless of causality. Changes in any protocol-specific systemic parameter evaluated during the study are to be reviewed by the Investigator.

## 7.3.3 RECORDING

AEs will be collected and recorded for any untoward event that occurs in a patient from the time he or she signs the Informed Consent for the trial until the end of the follow up period. Thus, any untoward medical occurrences or unfavorable and unintended signs, symptoms, or diseases that occur in the pretreatment, in treatment, or post treatment period are to be considered AEs and/or SAEs, and consequently recorded and reported as such. Should a non-serious AE become serious, the Investigator will then follow the same reporting procedures as for SAEs.

Each AE will be described by:

- Its duration (start and stop dates).
- Its seriousness.
- Its relationship to the study drug (suspected/unsuspected).
- Action(s) taken.
- Outcome.

Medical conditions/diseases and related signs/symptoms present before starting study treatment shall be documented in the medical history section of the CRF; these conditions are considered AEs only if they increase either in frequency or severity once informed consent has been signed.

# 7.3.4 RELATIONSHIP AND SEVERITY OF AES TO THE INVESTIGATIONAL PRODUCT

The Investigator will assess the possible relationship between the AE and the investigational medication, according to the criteria in Table below:

None (Intercurrent Event)	An event that is not and cannot be related to the Investigational Product, e.g. patient is a passenger in a road traffic accident.
Unlikely (remote)	Relationship is not likely e.g. a clinical event including laboratory test abnormality with temporal relationship to drug administration which makes a causal relationship improbable and in which other drugs, chemicals or underlying disease provide more plausible explanations
Possible	Relationship may exist, but could have been produced by the patient's condition or treatment or other cause
Probable	Relationship is likely, the AE abates upon discontinuation of Investigational Product and cannot be due to the patient's condition
Highly Probable	Strong relationship, the event abates upon discontinuation of Investigational Product and, if applicable, re-appears upon repeat exposure

The Investigator will grade the severity of any AE using the definitions in the Table below. For each episode, the highest severity grade attained should be reported.

#### Severity of the Adverse Event

Mild	Grade 1 - Does not interfere with patient's usual function (awareness of symptoms or signs, but easily tolerated [acceptable]).
Moderate	Grade 2 - Interferes to some extent with patient's usual function (enough discomfort to interfere with usual activity [disturbing]).
Severe	Grade 3 - Interferes significantly with patient's usual function (incapacity to work or to do usual activities [unacceptable])

#### 7.3.5 FOLLOW-UP OF PATIENTS WITH ADVERSE EVENTS

The Investigator is responsible for adequate and safe medical care of subjects during the trial and for ensuring that appropriate medical care and relevant follow-up procedures are maintained after the trial. All AEs should be followed-up to determine outcome of the reaction. The Investigator should follow up the event until resolution or stabilization of the condition. It is the Investigator's responsibility to ensure that the subjects experiencing AEs receive definite treatment for any AE, if required.

If subject was hospitalized due to a SAE, a copy of the discharge summary is to be forwarded to the Sponsor as soon as it becomes available.

In addition, a letter from the Investigator that summarizes the events related to the case as well as results of any relevant laboratory tests also may be requested. Further, depending upon the nature of the SAE, Dompé may request copies of applicable segments of the patient's medical records. In case of death, a copy of the autopsy report, if performed, should also be provided.

The Investigator shall inform the Sponsor with an appropriate written communication, whenever he becomes aware of new available information regarding the SAE, once the condition is resolved or

stabilized and when no more information about the event is expected. Follow-up SAE information should be processed as initial SAE notification (see Par. 7.3.6).

For pharmacovigilance purposes, all SAEs should be followed-up in order to clarify as completely as possible their nature and/or causality and until all queries have been resolved. All SAEs will be followed up until the events resolve or the events or sequelae stabilize, or it is unlikely that any additional information can be obtained after demonstration of due diligence with follow-up efforts (i.e. subject or Investigator is unable to provide additional information, or the subject is lost to follow up), unless subject has withdrawn his/her consent.

# 7.3.6 SERIOUS ADVERSE EVENT REPORTING

#### **Reporting Procedure for Investigators**

The Investigator must report all SAEs, regardless of presumed causal relationship, to Dompé Pharmacovigilance Department, preferably by e-mail (to [contact]) or [contact]) within 24 hours of learning of the event. Contact details for SAE reporting are provided in the section "Contact Information".

The investigator should also report information on SAEs that continue after patient has completed his/her participation in the study (whether study completion or withdrawal) unless patient has withdrawn his/her consent.

Information on SAEs will be recorded on the SAE form. Follow-up reports (as many as required) should be completed and e-mailed /faxed following the same procedure above, marking the SAE form as "follow up Number XX".

Whenever more than one SAE is observed, the Investigator should identify which is the primary adverse event, i.e. the most relevant one. If other events are listed in the same report, the Investigator, along with their relatedness to the Investigational Product, should identify which adverse events are serious and which are non-serious. In any case, the Investigator is requested to record his/her opinion about the relatedness of the observed event(s) with the investigational medication.

In line with CT3 Detailed Guidance and ICH E2A provisions, although the Investigator does not usually need to actively monitor patients for AEs once the trial has ended, if the Investigator becomes aware of a SAE occurring to a patient after that patient has ended his/her participation in the study (whether study completion or withdrawal), the SAE should be reported by the Investigator to Dompé Pharmacovigilance. Such "post-study cases" should be regarded for expedited reporting purposes by Dompé, as though they were study reports. Therefore, a causality assessment and determination of expectedness are needed for a decision on whether or not expedited reporting is required.

The following situation shall not be considered SAE:

• Abnormal lab values or test results that do not induce clinical signs and/or symptoms and require intervention/therapy, i.e. are clinically significant.

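### Read literally, the only exclusion in Protocol section 7.3.6 removes asymptomatic, clinically significant laboratory abnormalities that need therapy from SAE status, and so conflicts with section 7.3.1

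*Protocol*

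**What the plan says.** Protocol section 7.3.6 sets the investigator's duty: "The Investigator must report all SAEs, regardless of presumed causal relationship", and it must be done "within 24 hours of learning of the event". The section ends with an exclusion introduced by "The following situation shall not be considered SAE". It has a single item: "Abnormal lab values or test results that do not induce clinical signs and/or symptoms and require intervention/therapy, i.e. are clinically significant".

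Protocol section 7.3.1 gives the definitions. An AE can be "any unfavourable and unintended sign (including an abnormal laboratory finding), symptom, or disease". Among the seriousness criteria is the important medical event, which on appropriate medical judgment "may jeopardize the patient and may require medical or surgical intervention to prevent one of the outcomes listed above". One of the examples is "blood dyscrasias or convulsions that do not result in patient hospitalization".

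The classification as serious then feeds two later steps. Protocol section 7.3.7 sets 7-day and 15-day limits for submitting SUSARs, which by definition are serious. SAP section 8.1 plans tables of serious TEAEs and counts of serious ADRs.

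**The concern.** An exclusion of this kind normally spares sites from reporting trivial laboratory deviations. This one describes the opposite group. Its closing gloss asserts clinical significance where one would expect a denial, and it joins the absence of signs or symptoms to the presence of a need for therapy.

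An asymptomatic laboratory abnormality that is treated to prevent something worse is a natural candidate for the important-medical-event criterion. An investigator holding such a result finds two instructions. Section 7.3.1 says to judge whether it is serious. Section 7.3.6, which is where one looks when deciding whether the 24-hour clock has started, says that it is not an SAE. If the second is followed, the event does not go to pharmacovigilance as an SAE, is not assessed as a possible SUSAR, and is missing from the serious-event tables.

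**Working it through.** The plan gives no figure on this point, so the check is one of logic and text.

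**Step 1: what the bullet removes.** Let A mean that the value induces clinical signs or symptoms, and B that it requires intervention or therapy. Three readings are possible:

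- Literal: not A, and B. The words are taken as they stand.
- Joint negation: not (A and B). The negative is taken to govern both conditions together.
- Probably intended: neither A nor B, and hence not clinically significant. This needs a negative that the text does not contain.

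| Laboratory value | Literal | Joint negation | Probably intended |
|---|---|---|---|
| Signs or symptoms, needs therapy | not removed | not removed | not removed |
| Signs or symptoms, no therapy | not removed | removed | not removed |
| No signs or symptoms, needs therapy | **removed** | **removed** | not removed |
| No signs or symptoms, no therapy | not removed | removed | removed |

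The third row is the critical case. It loses SAE status under both readings that the printed words can bear, and keeps it only if the reader supplies the missing negative. The first row is safe under every reading. The literal reading also fails to exclude the harmless group in the fourth row, which supports the view that this is a drafting slip.

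**Step 2: comparison with the SAE definition.** The important-medical-event criterion in section 7.3.1 does not require symptoms. It turns on possible jeopardy to the patient and a possible need for intervention to prevent a serious outcome. Blood dyscrasias, which can be laboratory-based, are among its examples, and the AE definition expressly covers laboratory findings. So some values in the third row can be SAEs under 7.3.1. Not all are: the criterion depends on medical judgment, and a need for therapy alone does not make a value serious. The two sets overlap; they do not coincide.

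**Step 3: precedence.** Neither section says which governs. The rule in 7.3.1 for cases of doubt concerns only whether hospitalization occurred.

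**Step 4: what is affected and what is not.**

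- Affected if 7.3.6 is followed: the 24-hour report (section 7.3.6), the SUSAR assessment (section 7.3.7), and the serious-TEAE and serious-ADR outputs (SAP section 8.1).
- Still available: recording as an AE (section 7.3.1); the laboratory tabulations in Protocol section 9.4.3 and SAP section 8.2; and the adverse-event and laboratory analyses given to the DMC at each Safety Integrity Review (SAP section 4.6).

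These routes have limits. Protocol section 9.4.3 promises counts of abnormal clinically significant values, whereas SAP section 8.2 tabulates only whether a value is out of the normal range. An LDH above normal is itself one way to meet an entry criterion (section 5.2), so a bare out-of-range flag says little for that test. Severity in section 7.3.4 is graded by interference with usual function, so a silent laboratory event would tend to be graded low. Section 10.3 rules out on-site monitoring.

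**The case against.** The best defence is that this is an evident slip. An experienced investigator would supply the missing negative, would still have 7.3.1 in hand, and might have clear instructions in the SAE form and completion guideline of Appendix 5, a separate document not available here. Laboratory data also reach the DMC whatever the SAE label. All of this is fair, and it means that one cannot say such events will go unreported, only that they may. It does not rescue the rule. Two of the three readings remove the critical case, and a mandatory reporting rule should not depend on sites correcting it for themselves.

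A reader might infer more than the documents support:

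- *That all clinically significant laboratory values are excluded.* The bullet is limited to values without clinical signs or symptoms.
- *That sedated patients widen the gap because they cannot report symptoms.* The bullet also refers to signs, which staff observe.
- *That the serious gastrointestinal bleeding with anaemia in section 10.1.4 shows what would be missed.* That patient had nausea, vomiting and severe bleeding, so the bullet would not apply. She had also received three times the foreseen dose in error, and section 7.3.10 sends overdoses through the 24-hour SAE procedure in any case.
- *That the hepatic and renal exclusion criteria mark those organs as drug risks.* The protocol gives no such reason for them.
- *That the DMC would be blind to these events.* SAP section 4.6 provides it with laboratory analyses, including longitudinal ones.
- *That events have already been suppressed.* Nothing in the documents shows this.

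**Conclusion.** The point holds as an internal contradiction in an operative safety-reporting rule. As printed, the 7.3.6 bullet withdraws SAE status from asymptomatic laboratory abnormalities that need therapy and are clinically significant, and some of these can qualify as SAEs under 7.3.1. The error runs in the unsafe direction, and the sections must be reconciled.

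No size can be given. It is tempting to reason from the 32 reparixin patients planned in phase 2: one event is 1/32 = 3.1%, and zero events leave a one-sided 95% upper limit of 1 − 0.05^(1/32) = 8.9%. Those figures describe any arm of 32 patients. They do not measure how many events this wording would misclassify, which the documents do not reveal.

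The conclusion assumes that sites may apply the text as printed and that Appendix 5 does not already correct it. If Appendix 5 does, the practical risk is smaller, but the protocol still contradicts itself.

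**What to change.** Reword the bullet in section 7.3.6 so that a laboratory value or test result is excluded only when all four of these hold: it causes no clinical signs or symptoms; it does not require intervention or therapy; it is not clinically significant; and it meets no seriousness criterion in section 7.3.1. Add that 7.3.1 prevails if the two sections conflict. Notify sites of the correction, and check that the Appendix 5 completion guideline says the same.

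The cost is a small protocol correction, a letter to sites and slightly more SAE forms. Treatment, randomization and the planned analyses do not change.
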